7.11.3 Outliers

All values will be included in the analyses.

7.11.4 Visit Windows

The acceptable time ranges of the efficacy and safety examinations, observations, etc. from the date of initial study treatment (Day 1) are defined as follows. If there are multiple data available over the same period of time, the data obtained on the date closest to the reference date will be utilized; the later date will be applied if the number of days from the reference date is equal. Subjects who have no evaluable post-dose data on ACR20, ACR50, and ACR70 response rates will be counted as non-responders and included in the analysis at the end of Week 12 (Week 12 or at early termination before Week 12).

7.11.5 Handling of Schedule of Assessments of Efficacy Variables

For data obtained after the end of study treatment, the data obtained within + 2 days after the last dose is taken will be included in analysis. For data after the end of reference treatment, data obtained within + 9 days after the last dose will be included in analysis. Baseline for efficacy is defined as value at Day 1 before the first dose of study drug or reference drug for all subjects including placebo assigned subjects. For Week 12/ET, the values at closest date to reference date will be used. As for the subjects who switched to receive ASP015K instead of placebo, the last observation before first dose of ASP015K at Week 12 will be used for the analysis for visit Week 4, 8, 12, 12/ET. For EOT, the closest value to the reference date will be used regardless of the switching from placebo.

- (1) TJC (68 joints)/SJC (66 joints), laboratory test (CRP)

Table 9. Visit Window for TJC (68 joints)/SJC (66 joints), laboratory test (CRP)

Time points defined in analysis	Reference date*	Acceptable time range
Screening**	Day -28 to Day -1	Day -28 to Day -1
Baseline	Day 1	Day 1
Week 4 to Week 48***	Day $7 \times x + 1$	Day $(7 \times x - 6)$ to Day $(7 \times x + 8)$ and before the initiation of treatment with the study drug or reference drug on the visit day
Week 52	Day 365	Day 358 to Day 372
Week 12/ET (Week 12 or at early termination before Week 12)	Day 85	Day 2 to Day 92
EOT (Week 52 or at early termination)	Day 365	Day 2 to Day 372

*: Day 1 represents the first day of study or reference treatment. The day before the initiation of treatment with the study drug or reference drug is expressed as Day -1.

** : PGA, SGA, subject's assessment of pain, and CRP are not applicable.

***: Represents the reference date and acceptable time range for Week x.

- (2) PGA and SGA (VAS), subject's assessment of pain (VAS), HAQ-DI, laboratory test (ESR)

Table 10. Visit Window for PGA and SGA (VAS), subject's assessment of pain (VAS), HAQ-DI, laboratory test (ESR)

Time points defined in analysis	Reference date*	Acceptable time range
Baseline	Day 1	Day 1
Week 4 to Week 48**	Day $7 \times x + 1$	Day $(7 \times x - 6)$ to Day $(7 \times x + 8)$ and before the initiation of treatment with the study drug or reference drug on the visit day
Week 52	Day 365	Day 358 to Day 372
Week 12/ET (Week 12 or at early termination before Week 12)	Day 85	Day 2 to Day 92
EOT (Week 52 or at early termination)	Day 365	Day 2 to Day 372

*: Day 1 represents the first day of study or reference treatment. The day before the initiation of treatment with the study drug or reference drug is expressed as Day -1.

** : Represents the reference date and acceptable time range for Week x.

(3) SF-36 v2[®], WPAI

Table 11. Visit Window for SF-36 v2[®], WPAI

Time points defined in analysis	Reference date*	Acceptable time range
Baseline	Day 1	Day 1
Week 4 to Week 28**	Day $7 \times x + 1$	Day $(7 \times x - 6)$ to Day $(7 \times x + 8)$ and before the initiation of treatment with the study drug or reference drug on the visit day
Week 52	Day 365	Day 358 to Day 372
Week 12/ET (Week 12 or at early termination before Week 12)	Day 85	Day 2 to Day 92
EOT (Week 52 or at early termination)	Day 365	Day 2 to Day 372

*: Day 1 represents the first day of study or reference treatment. The day before the initiation of treatment with the study drug or reference drug is expressed as Day -1.

** : Represents the reference date and acceptable time range for Week x.

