Design and Methodology:	This is a multi-center, randomized, placebo-controlled, double-blind, parallel-group, confirmatory study to evaluate the efficacy and safety of ASP015K alone or in combination with DMARDs, at doses of 100 mg and 150 mg, in patients with RA who had an inadequate response to DMARDs. Etanercept will also be administered as the reference drug. In the study, ASP015K (test drug) and placebo (comparative drug) will be given as study drugs, and etanercept will be given as a separate reference drug. After screening, subjects will be randomized at baseline in a 1:1:1:2 ratio to the ASP015K 100 mg group, ASP015K 150 mg group, placebo group, or reference group in each study region. The study drug will be orally administered once daily (QD) after breakfast for 52 weeks. Etanercept will be administered subcutaneously once weekly for 52 weeks (the last dose will be given at Week 51). At Week 12, subjects in the placebo group will be switched to either ASP015K 100 mg or ASP015K 150 mg, and the dose will be maintained until the end of treatment. The dose of ASP015K (100 or 150 mg) to be started at Week 12 for the placebo group will be determined randomly at baseline in advance and switched in a blinded manner. Dynamic allocation procedures in each study region (Japan, Korea and Taiwan) will be used at randomization at baseline, with the study center, prior biologic-DMARD-IR, and concomitant DMARD use at the initiation of treatment with the study drug or reference drug as covariates. An anti-TNF agent, etanercept, will be administered as the reference drug in an open-label manner. Subjects in the ASP015K 100 mg, ASP015K 150 mg, or placebo groups who have completed the study will be eligible for participation in an open-label extension study (015K-CL-RAJ2). Subjects will make a follow-up visit after the Week 52 visit if they do not enroll into the extension study on the day of the Week 52 visit.
Number of Subjects to Be Enrolled/Randomized:	One-hundred subjects per group will receive the study drug and 200 subjects the reference drug (a total of 500 subjects).

- CONFIDENTIAL -

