The reference drug will be subcutaneously administered to subjects once weekly (the last dose will be given at Week 51). The baseline dose should be given at each study center on the day of the baseline visit after all assessments and tests are completed. After the baseline visit, the reference drug will be given taking the same day of the week at baseline as the reference date. The acceptable time range for administration of the reference drug will be within ± 6 days of the reference date, and if the reference drug is given beyond the acceptable time range, it will be regarded as unadministered. The reference drug should also be administered at a minimum of 3-day intervals.

Doses on the day of scheduled visits during treatment with the study drug or reference drug should be given on the day of the visit after all assessments and tests are completed.

The reference drug may be given at any time on administration days (in-hospital administration and self-administration), except those of scheduled visits.

Etanercept can be self-administered only by the subject who has been provided with adequate education and training by the study center and who is judged to be capable of injecting etanercept by himself/herself in the opinion of the investigator/sub-investigator.

The investigator/sub-investigator should instruct subjects who will self-administer etanercept to pay close attention to their condition before and after administration on the day of self-administration to assess the condition in a prompt manner. When the investigator/sub-investigator finds problems with the subject's adherence to self-injection treatment regimens and the mode of administration, the investigator/sub-investigator will administer etanercept at the hospital until the subject can learn to inject it by himself/herself.

The subject's condition before and after in-hospital administration should also be closely monitored.

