7.9.1 Handling of Schedule of Assessments of Efficacy Variables

For data after the end of study treatment, data obtained within + 2 days after the last dose is taken will be included in analysis. For data after the end of reference treatment, data obtained within + 9 days after the last dose will be included in analysis.

- CONFIDENTIAL -

(1) TJC (68 joints)/SJC (66 joints), laboratory test (CRP)

Time points defined in analysis	Reference date*	Acceptable time range
Screening	Day -28 to Day -1	Day -28 to Day -1
Baseline	Day 1	Day 1
Week 4 to Week 48**	Day $7 \times x + 1$	Day $(7 \times x - 6)$ to Day $(7 \times x + 8)$ and before the initiation of treatment with the study drug or reference drug on the visit day
Week 52	Day 365	Day 358 to Day 372
End of Week 12 (Week 12 or at early termination before Week 12)	Day 85	Day 2 to Day 92
End of treatment (Week 52 or at early termination)	Day 365	Day 2 to Day 372

*: Day 1 represents the first day of study or reference treatment. The day before the initiation of treatment with the study drug or reference drug is expressed as Day -1.

** : Represents the reference date and acceptable time range for Week x.

(2) PGA and SGA (VAS), subject's assessment of pain (VAS), HAQ-DI, laboratory test (ESR)

Time points defined in analysis	Reference date*	Acceptable time range
Baseline	Day 1	Day 1
Week 4 to Week 48**	Day $7 \times x + 1$	Day $(7 \times x - 6)$ to Day $(7 \times x + 8)$ and before the initiation of treatment with the study drug or reference drug on the visit day
Week 52	Day 365	Day 358 to Day 372
End of Week 12 (Week 12 or at early termination before Week 12)	Day 85	Day 2 to Day 92
End of treatment (Week 52 or at early termination)	Day 365	Day 2 to Day 372

*: Day 1 represents the first day of study or reference treatment. The day before the initiation of treatment with the study drug or reference drug is expressed as Day -1.

** : Represents the reference date and acceptable time range for Week x.

(3) SF-36 v2[®], WPAI

Time points defined in analysis	Reference date*	Acceptable time range
Baseline	Day 1	Day 1
Week 4 to Week 28**	Day $7 \times x + 1$	Day $(7 \times x - 6)$ to Day $(7 \times x + 8)$ and before the initiation of treatment with the study drug or reference drug on the visit day
Week 52	Day 365	Day 358 to Day 372
End of Week 12 (Week 12 or at early termination before Week 12)	Day 85	Day 2 to Day 92
End of treatment (Week 52 or at early termination)	Day 365	Day 2 to Day 372

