3.2 Study Design

This is a Japanese, Korean and Taiwanese, multi-center, randomized, placebo-controlled, double-blind, parallel-group, confirmatory study to evaluate the efficacy and safety of ASP015K alone or in combination with DMARDs, at doses of 100 mg/day and 150 mg/day, in patients with RA who had an inadequate response to DMARDs. Open-label etanercept will also be administered as the reference drug for 52 weeks (the last dose will be given at Week 51). In the study, ASP015K (test drug) and placebo (comparative drug) will be given as study drugs, and etanercept will be given as a separate reference drug. DMARD response is evaluated at the initiation of screening and then after the screening period, subjects will be randomized in a 1:1:1:2 ratio to the ASP015K 100 mg, ASP015K 150 mg, placebo, or reference groups, and they will receive either the study drug or reference drug for 52 weeks. Subjects in the ASP015K 100 mg, ASP015K 150 mg, and placebo groups will orally receive either ASP015K or placebo once daily after breakfast, while those in the reference group will receive 50 mg of subcutaneous etanercept once weekly.

The planned sample size is 100 subjects each for the ASP015K 100 mg, ASP015K 150 mg, and placebo groups and 200 subjects for the reference group.

Re-screening is allowed only in situations in which a subject underwent the screening procedures (i.e., scans and laboratory work) and owing to logistical circumstances, the allocated time window for these tests has expired. Re-screening is not permitted in cases in which the initial test results do not support eligibility based on inclusion and exclusion criteria. The subject must be classified as a screening failure at that time point.

Based on the consideration of the ethical issues related to long-term placebo use, at Week 12 subjects in the placebo group will be switched to either ASP015K 100 mg or ASP015K 150 mg, and the dosage will be maintained until the end of treatment. The ASP015K dose that will be started for placebo group subjects at Week 12 (100 or 150 mg) will be randomly chosen at baseline. The dose will be switched under the blinded condition.

Subjects in the ASP015K 100 mg, ASP015K 150 mg, or placebo groups who complete this study will be eligible for participation in the open-label extension study (015K-CL-RAJ2). Subjects will make a follow-up visit after the Week 52 visit if they do not enroll into the extension study on the day of the Week 52 visit.

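### The +9-day cut-off for etanercept excludes some Week 52 visits that lie inside the plan's own Week 52 window

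*SAP*

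**What the plan says.** SAP 3.2 states of etanercept that "the last dose will be given at Week 51", and the protocol agrees. Protocol 5.1.1 ties the injections to the calendar and not to the visit: "the reference drug will be given taking the same day of the week at baseline as the reference date". It also gives a tolerance: "The acceptable time range for administration of the reference drug will be within ± 6 days of the reference date".

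SAP 7.11.5 limits data collected after treatment ends. For the oral arms, "the data obtained within + 2 days after the last dose is taken will be included in analysis". For the reference arm, "For data after the end of reference treatment, data obtained within + 9 days after the last dose will be included in analysis". Table 9 in the same section sets the Week 52 window, for every arm, at "Day 358 to Day 372". The EOT window also ends on Day 372, and EOT takes the value closest to Day 365.

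The same limits appear for safety (SAP 7.11.6) and PD (SAP 7.11.7), and in Protocol 7.9.1 to 7.9.3; for the reference arm Protocol 7.9.1 reads "data obtained within + 9 days after the last dose will be included in analysis". No section exempts subjects who complete treatment, and none says whether the cut-off or the visit window takes precedence.

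**The concern.** For a subject who stops early, a limit on time since last dose keeps off-treatment values out of the summaries. For an etanercept completer, the planned schedule already puts a week between the last dose and the Week 52 visit. The limit therefore uses up most of its nine days before the visit falls due, and a visit that is late but permitted can fail it.

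At stake are the Week 52 and EOT columns of the efficacy, by-visit safety and PD tables, where Appendices 2 and 4 of the SAP set the 100 mg, 150 mg and reference groups side by side. Followed exactly, the plan drops valid reference-arm values because of visit timing. EOT for those subjects then comes from a visit that may be months earlier.

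**Working it through.** **Inputs.** Day number for Week x is 7x + 1 (SAP Table 9). Last etanercept dose is at Week 51 (SAP 3.2), with a tolerance of ±6 days (Protocol 5.1.1). Cut-offs are +9 days (reference) and +2 days (oral) (SAP 7.11.5).

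**The plan's own figures.** Week 52 = 7 × 52 + 1 = Day 365, and ±7 gives Days 358 to 372, as in Table 9. Week 51 = 7 × 51 + 1 = Day 358. Adding 7 gives Day 365, which agrees with the compliance rule in SAP 6.5 that treats the Week 52 visit as the Week 51 dose plus 7 days.

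**Reference arm.** Cut-off = last dose + 9. A visit is lost if it lies in Days 358 to 372 but after the cut-off. The tolerance allows a last dose from 358 − 6 = Day 352 to 358 + 6 = Day 364.

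| Last dose | Cut-off | Window days lost (of 15) | Day 365 kept? |
|---|---|---|---|
| Day 352 | Day 361 | 362–372 (11) | No |
| Day 355 | Day 364 | 365–372 (8) | No |
| Day 356 | Day 365 | 366–372 (7) | Yes |
| **Day 358 (on schedule)** | **Day 367** | **368–372 (5)** | **Yes** |
| Day 362 | Day 371 | 372 (1) | Yes |
| Days 363–364 | Days 372–373 | none | Yes |

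Because doses follow the baseline weekday, a late visit does not carry the last dose with it. The five-week maximum visit interval (Protocol 5.1.6) does not rule out the late days: from a Week 48 visit on Day 337, 337 + 35 = Day 372.

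**Oral arms.** SAP 6.5 counts planned tablets to the day before the Week 52 visit. The Week 52 trough sample needs a dose 19 to 29 hours earlier (protocol section VI). Each pack holds 28 + 7 = 35 days of tablets (Protocol 4.2), which matches the five-week maximum interval. The gap from last dose to visit is thus 1 day, inside the 2 allowed, and none of the 15 window days is lost.

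**How many subjects.** The documents give no spread of visit dates, so this is illustration only. Assume the last dose on Day 358 and visit days normally distributed around Day 365 with standard deviation s, rounded to whole days. The first excluded day is 368, so the share lost is P(Z > (367.5 − 365)/s) = P(Z > 2.5/s).

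| s (days) | 2.5/s | Share lost |
|---|---|---|
| 1 | 2.50 | about 0.6% |
| 1.5 | 1.67 | about 5% |
| 2 | 1.25 | about 11% |
| 3 | 0.83 | about 20% |

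**What replaces the lost visit.** The Table 8 imputation methods are titled for Week 12/ET, so an excluded Week 52 value appears to stay missing. EOT falls back to the last scheduled assessment before Week 52 in the Schedule of Assessments:

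- Week 48: joint counts, VAS scores, CRP and ESR, HAQ-DI, routine laboratory tests.
- Week 40: fasting lipids, body weight.
- Week 28: SF-36v2, WPAI, biomarkers and lymphocyte subsets, 12-lead ECG.

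**The case against.** The best defence is that the cut-off is a deliberate on-treatment rule. Nine days looks like one 7-day dosing interval plus the 2 days allowed for daily tablets. That is an inference, but the exposure and PPS duration rules show a similar offset, adding 8 days for etanercept and 1 for tablets. On this view the arms are treated alike in time beyond the dosing interval, and an on-schedule subject keeps any visit up to 2 days late. This stands as an account of where the number came from, and equalising time off drug is a legitimate choice. It does not settle the conflict: the plan also declares Days 368 to 372 acceptable for Week 52 and does not rank the two rules.

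The oral arms are not immune. A subject in a permitted suspension (up to 7 days) or interruption (up to 28 days) at Week 52 can exceed +2 days and be cut. That is correct, so the asymmetry concerns subjects who are dosing as planned.

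The affected tables are secondary. Treatment comparisons in the SAP are against placebo, the reference arm is open-label, and Week 52 efficacy is summarised without testing. That also stands and limits the importance of the point.

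Finally, widening acceptance for completers admits values further from the last dose. That is a real cost and belongs in the fix.

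**Conclusion.** The cut-off and the Week 52 window contradict each other for the reference arm. With the last dose on schedule, 5 of 15 permitted visit days are lost. With a last dose 3 to 6 days early, an on-time visit is lost too. Oral completers who dose to the day before the visit lose none. This last statement rests on the SAP compliance formula, the trough requirement and the tablet supply. If oral dosing stopped strictly on Day 364, its cut-off would be Day 366 and Days 367 to 372 would be lost there too, but the documents do not support that reading.

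A reader might infer more, in three ways:

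- That a known and sizeable fraction of etanercept completers loses Week 52. The documents give neither visit-date nor dose-date spread, and under the assumptions above the share runs from about 0.6% to about 20%. The 5 of 15 is a count of days, not a frequency.
- That all reference-arm Week 52 data are at risk. On-time visits after an on-schedule dose are kept.
- That the trial's main conclusions are exposed. The Week 12 primary analysis is unaffected. TEAEs follow their own definitions, and laboratory minimum and maximum over the entire period carry no date limit. The effect is confined to descriptive Week 52 and EOT efficacy, by-visit safety and PD summaries.

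**What to change.** In SAP 7.11.5, 7.11.6 and 7.11.7, and in Protocol 7.9.1 to 7.9.3, state that the +2-day and +9-day limits apply only to subjects who discontinue treatment early. For subjects who complete treatment, accept the Week 52 visit anywhere in Days 358 to 372, for both Week 52 and EOT, in all arms.

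The text cost is about one sentence per section, and no new data are needed. The analytic cost should be stated openly. The added etanercept values will lie 368 − 358 = 10 to 372 − 358 = 14 days after an on-schedule last dose, up to 372 − 352 = 20 days after the earliest permitted one, and longer after an interruption. Oral completers in a suspension or interruption at Week 52 would also be counted. To let readers judge this, either report time since last dose at Week 52 by arm, or give the Week 52 summary under the +2/+9-day cut-offs as a supplementary table.

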7.11.6 Handling of Schedule of Assessments of Safety Variables

For data obtained after the end of study treatment, the data obtained within + 2 days after the last dose is taken will be included in analysis. For data after the end of reference treatment, data obtained within + 9 days after the last dose will be included in analysis. Baseline for safety is defined as last non-missing value before the first dose of study drug or reference drug for all subjects including placebo assigned subjects. For Week 12/ET, the values at closest date to reference date will be used. As for the subjects who switched to receive ASP015K instead of placebo, the last observation before first dose of ASP015K at Week 12 will be used for the analysis for visit Week 4, 8, 12, 12/ET. For EOT, the closest value to the reference date will be used regardless of the switching from placebo.

- (1) Physical examination, vital signs, laboratory test [hematology, biochemistry, urinalysis, and pregnancy test (serum and urine)]

Table 12. Visit Window for Physical examination, vital signs, laboratory test (hematology, biochemistry, urinalysis, and pregnancy test (serum and urine))

Time points defined in analysis	Reference date*	Acceptable time range
Screening	Day -28 to Day -1	Day -28 to Day -1
Baseline	Day 1	Day 1
Week 4 to Week 48**	Day $7 \times x + 1$	Day $(7 \times x - 6)$ to Day $(7 \times x + 8)$ and before the initiation of treatment with the study drug or reference drug on the visit day
Week 52	Day 365	Day 358 to Day 372
Minimum on Treatment up to Week 12***		Minimum value at allowance Range (Day 2 to Day 92) before first dose of Week 12 study drug
Maximum on Treatment up to Week 12***		Maximum value at allowance Range (Day 2 to Day 92) before first dose of Week 12 study drug
Minimum on Treatment***		Minimum value during Entire Period (No limitation for period)
Maximum on Treatment***		Maximum value during Entire Period (No limitation for period)
Week 12/ET (Week 12 or at early termination before Week 12)	Day 85	Day 2 to Day 92
EOT (Week 52 or at early termination)	Day 365	Day 2 to Day 372

*: Day 1 represents the first day of study or reference treatment. The day before the initiation of treatment with the study drug or reference drug is expressed as Day -1.

** : Represents the reference date and acceptable time range for Week x.

***: Applied to laboratory test only.

(2) Laboratory test (fasting lipid profile test)

Table 13. Visit Window for Laboratory test (fasting lipid profile test)

Time points defined in analysis	Reference date*	Acceptable time range
Baseline	Day 1	Before the initiation of treatment with the study drug or reference drug on Day 1 and at least 8 hours after the last meal If Baseline data is not measured at Day 1, then the closest day up to Day 1 after Day -28 will be used for Baseline.
Week 12	Day 85	Day 78 to Day 92
Week 20	Day 141	Day 134 to Day 148
Week 28	Day 197	Day 190 to Day 204
Week 40	Day 281	Day 274 to Day 288
Week 52	Day 365	Day 358 to Day 372
Minimum on Treatment up to Week 12		Minimum value at allowance Range (Day 2 to Day 92) before first dose of Week 12 study drug
Maximum on Treatment up to Week 12		Maximum value at allowance Range (Day 2 to Day 92) before first dose of Week 12 study drug
Minimum on Treatment		Minimum value during Entire Period (No limitation for period)
Maximum on Treatment		Maximum value during Entire Period (No limitation for period)
Week 12/ET (Week 12 or at early termination before Week 12)	Day 85	Day 2 to Day 92
EOT (Week 52 or at early termination)	Day 365	Day 2 to Day 372

*: Day 1 represents the first day of study or reference treatment. The day before the initiation of treatment with the study drug or reference drug is expressed as Day -1.

(3) 12-lead ECG, Chest radiography

Table 14. Visit Window for 12-lead ECG

Time points defined in analysis	Reference date*	Acceptable time range
Screening	Day -28 to Day -1	Day -28 to Day -1
Week 28	Day 197	Day 190 to Day 204
Week 52	Day 365	Day 358 to Day 372
EOT (Week 52 or at early termination)	Day 365	Day 2 to Day 372

*: Day 1 represents the first day of study or reference treatment. The day before the initiation of treatment with the study drug or reference drug is expressed as Day -1.

(4) Body weight

Table 15. Visit Window for Body weight

Time points defined in analysis	Reference date*	Acceptable time range
Screening	Day -28 to Day -1	Day -28 to Day -1
Week 12	Day 85	Day 78 to Day 92
Week 28	Day 197	Day 190 to Day 204
Week 40	Day 281	Day 274 to Day 288
Week 52	Day 365	Day 358 to Day 372
Week 12/ET (Week 12 or at early termination before Week 12)	Day 85	Day 2 to Day 92
EOT (Week 52 or at early termination)	Day 365	Day 2 to Day 372

*: Day 1 represents the first day of study or reference treatment. The day before the initiation of treatment with the study drug or reference drug is expressed as Day -1.

(5) QT assessment (except the reference group)

Table 16. Visit Window for QT assessment (except the reference group)

Time points defined in analysis	Reference date*	Acceptable time range
Baseline	Day 1	Day 1 Before the initiation of treatment with the study drug
Week 4 or 8 (before study drug administration)	Day 29 or Day 57	Before the initiation of treatment with the study drug on Reference date \pm 7
Week 4 or 8 (after study drug administration)	Day 29 or Day 57	2 hours post-dose (reference time, but within the range of 1 hour to 4 hours post-dose is acceptable) on Reference date \pm 7
Minimum on Treatment up to Week 12		Minimum value at allowance Range (Day 2 to Day 92) before first dose of Week 12 study drug
Maximum on Treatment up to Week 12		Maximum value at allowance Range (Day 2 to Day 92) before first dose of Week 12 study drug

*: Day 1 represents the first day of study or reference treatment. The day before the initiation of treatment with the study drug or reference drug is expressed as Day -1.

